2. STUDY ENDPOINTS

2.1 Primary and Secondary Endpoints: Double Blind and Open-Label Phases

Primary Efficacy Endpoint: Reduction at week 16 in the Ichthyosis Area Severity Index (IASI)

Primary Safety Endpoint: Occurrence of bacterial or fungal mucocutaneous infection through week 16

Secondary Efficacy Endpoints (evaluated at weeks 8, 12, 16, 32 and 52):

Product: Secukinumab

Protocol Number: CAIN457AUS05T

Date: 14 July 2018

15

- Reduction in the IASI-E at weeks 8,12 and 16 (double blind portion)
- Reduction in IASI-S at weeks 8,12 and 16 (double blind portion)
- Reduction in CISI (Congenital Ichthyosis Severity Index) for skin redness/ erythema at weeks 8,12 and 16 (double blind portion) by subject and by physician assessors
- Reduction in CISI (Congenital Ichthyosis Severity Index) for skin hyperkeratosis/ scaling at weeks 8,12 and 16 (double blind portion) by subject and by physician assessors
- Reduction in composite and erythema scores of Yale Ichthyosis Severity Index at weeks 8,12 and 16 (double blind portion)
- Reduction in the IASI-E at weeks 32 and 52 as compared to baseline (open label portion)
- Reduction in IASI-S at weeks 32 and 52 as compared to baseline (open label portion)
- Reduction in CISI (Congenital Ichthyosis Severity Index) for skin redness/ erythema by subject and by physician assessors at weeks 32 and 52 as compared to baseline (open label portion)
- Reduction in CISI (Congenital Ichthyosis Severity Index) for skin hyperkeratosis/ scaling by subject and by physician assessors at weeks 32 and 52 as compared to baseline (open label portion)
- Reduction in composite and erythema scores of Yale Ichthyosis Severity Index at weeks 32 and 52 as compared to baseline (open label portion)
- A 2-point reduction in CISI for redness/erythema at weeks 16, 32, and 52
- A 2-point reduction in CISI for scale/hyperkeratosis at weeks 16, 32, and 52
- A 50% reduction in IASI at weeks 16, 32 and 52
- A 50% reduction in IASI-E or IASI-S at weeks 16, 32 and 52
- A 75% reduction in composite and individual IASIs at weeks 16, 32 and 52
- 50% Reduction in the Bodemer score, which heavily weighs associated morbidity (contractures, ectropion, mouth tightness, fissures) in addition to erythema, scaling and thickening (Bodemer et al. 2011) at weeks 16, 32 and 52
- A 3-point reduction in patient-reported itch and pain (each on a 10 point scale) at weeks 16, 32 and 52
- Improvement in the 5-D itch score

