Index. CISI is a validated score that assesses individual scores for erythema, scaling and alopecia, but is limited in that it is not a single score, includes a feature found in the minority of patients (alopecia) and includes non-uniform Likert scales (0-4+ or 0-5+). M-CISI eliminates the alopecia score, adopts a 5-point Likert for erythema and scaling, and averages the erythema and scaling scores for a single global assessment; it is a new scale that is being validated herein but will not be used for endpoints. IASI is a composite score based on the global CISI score that captures differences in severity in different body regions as a function of their body surface area and also standardizes the number of choices within the Likert scales for erythema and scaling. As in the EASI score for AD and the PASI score for psoriasis, IASI evaluates erythema and scaling as 0-4+ in severity at each of 4 locations: head and neck (including scalp); arms (including palms); legs (including soles); and trunk, prorated based on body surface area in these sites and the percentage of involvement in each of these sites (total possible score for each is 24 and total composite score is 48). To include a patient-reported severity score, we will use the Congenital Ichthyosis Severity Index, which has been validated for patient use (Kamalpour et al 2010), and the m-CISI. We will also pilot in the US a complex, non-validated burden of disease scoring system proposed by Bodemer et al in France, which heavily weighs associated morbidity (contractures, ectropion, mouth tightness, fissures) in addition to other measures of severity. All investigators/ sub-investigators will be trained based on photographs before study initiation to uniformly assign CISI, m-CISI, Bodemer, and IASI scores. A huge issue is the paucity of validated scores for ichthyosis severity. Our evaluations will be performed concurrently (but without conferring) by two investigators to allow inter-rater reliability, as well as at screening and again at baseline (at 3-4 weeks to minimize recall bias) for assessing test-retest reliability. As such, we hope to use this opportunity to assess reliability in these un-validated instruments. Patient-reported itch will be quantified on a 0-10 numerical rating scale (NRS) and by 5-D itch score (Elman et al 2009); a 1-10 score pain assessment is part of the Bodemer scale. The Yale Severity Index was recently developed and tested at a recent meeting of the Foundation for Ichthyosis and Related Skin Types. It includes a 0-4+ scale for erythema and for scaling, and provides pictorial representations for comparison, dividing scaling into lamellar and keratoderma scale scores. This study is the first time it will be applied to patients in an investigation.

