To compare secukinumab to placebo according to the proportion of patients who achieve IASI50/IASI75 at week 16, a Fisher's exact test for contingency tables analysis will be used. The same approach will be used for all other binary outcomes, including a 2-point reduction in CISI, 50% (or 75%) reduction in IASI-E, EASI-S, a 3-point reduction in patient-reported itch or pain (each on a 10 point scale); and a 50% reduction in TEWL.

Mechanistic Endpoints: mRNA expression values will be normalized to housekeeping gene hARP and log₂-transformed for analysis. Measurements under the limit of detections will be imputed as 20% of the minimum value observed for that gene. Similar to the IASI score, qRT-PCR expression data was modeled using a mixed effect models.

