Appendix 5: Bodemer Scale

Product: Secukinumab
 Protocol Number: CAIN457AUS05T
 Date: 14 July 2018

(a) BODY SURFACE AREA WITH SCALES **(b) BODY SURFACE AREA WITH ERYTHEMA**

EXTENT: A =%

EXTENT: B =%

(c) PRURITUS: (C) (Value in cm)

PRURITUS (0 – 10) 0 _____ 10
 VISUAL ANALOGUE SCALE (average for the last 3 last days and nights)

(d) SKIN PAIN: (D) (Value in cm)

SKIN PAIN (0 – 10) 0 _____ 10
 VISUAL ANALOGUE SCALE (average for the last 3 last days and nights)

(e) SEVERITY OF 10 SYMPTOMS: (E) (Cumulated severity score for 10 symptoms: total value ranging from 0 to 60)

SCORE = A/10 + B/10 + C + D + E = / 100

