5. **Distribution:** Mark whether itching has been present in the following parts of your body over the last 2 weeks. If a body part is not listed, choose the one that is closest anatomically.

Head/Scalp		Soles	
Face		Palms	
Chest		Tops of Hands/Fingers	
Abdomen		Forearms	
Back		Upper Arms	
Buttocks		Points of Contact w/ Clothing (e.g waistband, undergarment)	
Thighs		Groin	
Lower legs			
Tops of Feet/Toes			

Product: Secukinumab

[figure not shown]
Protocol Number: CAIN457AUS05T

Date: 14 July 2018

[figure not shown]
55

Appendix 10

Numerical Rating Scale (NRS) for Pruritus (over past 3 days and nights)

Numerical Rating Scale (NRS) for Pain (over past 3 days and nights)

Product: Secukinumab

Protocol Number: CAIN457AUS05T

Date: 14 July 2018

56

[figure not shown]

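### The 3-point itch/pain responder endpoint needs one wording, one pain instrument and a denominator of patients able to respond

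*Combined protocol and SAP*

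**What the plan says.** Section 2.1 lists as a secondary endpoint "A 3-point reduction in patient-reported itch and pain (each on a 10 point scale) at weeks 16, 32 and 52". Section 9.3 analyses "a 3-point reduction in patient-reported itch or pain (each on a 10 point scale" among the binary outcomes, all compared by Fisher's exact test: "The same approach will be used for all other binary outcomes, including a 2-point reduction in CISI" and so on. Neither section says which form supplies the score.

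For itch, Section 6.1.9 states "Patient-reported itch will be quantified on a 0-10 numerical rating scale (NRS) and by 5-D itch score", and the synopsis lists an itch NRS. For pain, Section 6.1.9 says only that "a 1-10 score pain assessment is part of the Bodemer scale". Appendix 5 prints the Bodemer pruritus and pain items on 0 to 10 lines, each a "VISUAL ANALOGUE SCALE (average for the last 3 last days and nights"). Appendix 10 carries two further forms, "Numerical Rating Scale (NRS) for Pruritus (over past 3 days and nights") and "Numerical Rating Scale (NRS) for Pain (over past 3 days and nights"). The synopsis assessment list has no pain NRS, and the schedule in Appendix 1 has a row for itch scores but none that names pain.

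The severity entry criterion in Section 4.1 concerns IASI and erythema only. Section 9.1 defines one efficacy population, the mITT set of randomised patients who received at least one dose.

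**The concern.** A programmer cannot derive this endpoint without making undocumented choices: one endpoint or two, which pain form, and who belongs in the denominator. Section 9.3 plans an analysis of all data once the 16-week double-blind part is complete, so a choice still open at that time could be made with results in view.

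The denominator matters on its own account. A fixed-point responder definition has a floor: someone who starts with little itch or pain cannot improve by 3 points, whatever the drug does. Nothing in the eligibility criteria keeps such patients out, and no rule removes them from the proportion. They default to non-response in both arms, which lowers both rates and shrinks the difference at week 16. The same floor lowers the rates reported at weeks 32 and 52.

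**Working it through.** **The plan's own figure.** No sample size or response rate is stated for this endpoint. The only stated calculation is for IASI in Section 9.5, and it reproduces. SD of change = 9.0 × √(2 × (1 − 0.55)) = 8.54, stated as about 8.5. Difference = 0.30 × 28.9 = 8.67. Then n = 2 × (1.96 + 0.84)² × 8.5² / 8.67² = 15.1, so 16 per group, with power 79.7% by the noncentral t distribution. Allowing for dropout, 16 / 0.80 = 20 per group. Nothing below changes this.

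**Who cannot respond.** On a 0-10 scale a fall of 3 needs a baseline of at least 3. If pain really ran from 1 to 10, as Section 6.1.9 describes it, the threshold would be 4. The unresolved range therefore also changes who can respond.

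**Effect of the floor.** Inputs: 20 per arm (Section 9.5); two-sided 0.05, carried over from the primary test; and, as assumptions, response of 60% vs 15% among patients able to respond, with a share f in each arm starting below 3. Observed rate on all patients = (1 − f) × rate among those able to respond. For f = 40%: 0.6 × 60% = 36% and 0.6 × 15% = 9%, so a 45-point difference becomes 27 points. Power is exact: the binomial probabilities of all pairs of responder counts with a Fisher p-value of 0.05 or less are summed.

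| Share below 3 | Rates, all mITT | Difference (points) | Power, all 20 per arm | Able to respond per arm | Power, restricted |
|---|---|---|---|---|---|
| 0% | 60% vs 15% | 45 | 80% | 20 | 80% |
| 20% | 48% vs 12% | 36 | 63% | 16 | 64% |
| 40% | 36% vs 9% | 27 | 43% | 12 | 51% |
| 60% | 24% vs 6% | 18 | 23% | 8 | 31% |

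The restricted column fixes equal numbers able to respond in the two arms; in the trial they would vary.

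**The 2-point CISI responder.** The same floor applies to scaling, for which there is no entry minimum. The coding must be settled first: Section 6.1.9 describes CISI items as 0-4+ or 0-5+, whereas Appendix 3 numbers the scaling boxes 1 to 5 and the redness boxes 1 to 6. A cutoff of 3 would be right for boxes numbered from 1. On 0-4 coding it would wrongly exclude a patient at 2, who can fall to 0. Stated by position, the rule is the same under either coding: a two-category fall needs a baseline in the third category or higher. For redness the floor is unlikely to bind, because entry requires erythema described as at least moderate, and moderate redness is the fourth of six categories in Appendix 3.

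**The case against.** The strongest reply is that this is mostly loose wording. Scoring each symptom on its own 10-point scale suggests two endpoints, and Section 2.1 uses 'and' and 'or' loosely elsewhere when listing IASI subscores. That stands. A reader might infer two rival composites, both symptoms versus either symptom. If they were composites the gap would be large: with an assumed 40% response per symptom and latent correlation 0 to 0.7, 'both' gives 16-28% responders and 'either' 52-64%. With 50% vs 15% per symptom and 20 per arm, power would be 44-51% against 64-78%. But the documents never define a composite, and separate endpoints is the more natural reading, so these figures do not measure a defect in the plan.

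A reader might also infer that itch has two competing instruments, or that pain is never scheduled. Neither holds. The synopsis and Section 6.1.9 name the NRS for itch, and the Bodemer itch item belongs to a separately listed score. Section 6.1.9 cites Appendix 10 in its heading and places severity evaluations at every visit, so pain is scheduled even though no row of Appendix 1 names it.

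On the floor, the documents do not say that low-baseline patients are failures; that follows from the absence of any other rule. Randomisation balances such patients in expectation, Fisher's test stays valid, and an all-mITT proportion is a legitimate if diluted quantity. The gain from restriction is negligible at a 20% floor share. Section 9.1 also leaves room to document inclusion of subject data before the code is broken. All of this stands. It limits the point's weight but does not supply the missing definition.

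**Conclusion.** The point holds as a cheap improvement to a secondary endpoint. The two sections word the responder differently, and the pain instrument and its range are inconsistent across three places. With no itch or pain entry minimum and an mITT denominator, patients starting below 3 can only dilute the comparison. Under the assumed 60% vs 15%, restricting to patients able to respond raises power by about 1, 8 and 8 percentage points at floor shares of 20%, 40% and 60%. Power stays at 64% or less in each of these cases, so the main gain is a response rate that can be interpreted and was fixed in advance. All rates and floor shares here are assumptions, because the documents give no baseline itch or pain distribution. The documents do not support reading this as a threat to type I error, to the primary IASI analysis or to the sample size.

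**What to change.** In Sections 2.1 and 9.3, state two separate endpoints: a fall of at least 3 points in the Appendix 10 itch NRS, and a fall of at least 3 points in the Appendix 10 pain NRS, both scored 0-10. Keep the Bodemer VAS items for the Bodemer total only. Correct the 1-10 description of the Bodemer pain item in Section 6.1.9, and name the pain NRS in Appendix 1.

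Analyse each endpoint in mITT patients whose baseline score is at least 3. Report that number per arm, and give the all-mITT rate alongside. Fix this before the week-16 unblinded analysis.

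For the 2-point CISI scaling responder, first reconcile the coding in Section 6.1.9 with the numbering in Appendix 3. Then restrict to patients whose baseline is in the third category or higher. No restriction is needed for redness.

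The cost is protocol and SAP wording; the forms already exist. The downside is a smaller denominator for these endpoints. Because the subset is defined by a pre-randomisation value, the comparison within it remains randomised.

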- Tape strips to evaluate skin proteomics and lipidomics

Data Analysis

Statistical analysis of all clinical and translational studies will be performed by a statistician at the Icahn School of Medicine at Mount Sinai and .

The data from both centers that participate in this study will be combined for analyses. The primary analysis population will be based on a modified intention-to-treat (mITT) population, which is defined as all randomized patients who received at least one dose of the randomized treatment. Because the loading dose is given at baseline, this should effectively include all the randomized patients.

Efficacy and other data will be summarized. Descriptive statistics of demographics and other baseline characteristics will be presented for all subjects. For more details, refer to Section 9.2. The primary efficacy variable is the IASI (composite) at Week 16. The primary safety variable is the occurrence of bacterial and fungal mucocutaneous infections by Week 16. Differences in change over time between treatment and placebo will be assessed using a mixed-effect model repeated measures. Outcomes for weeks 0 to 16 for all the subjects from phase 1 and the outcomes for weeks 16 to 52 for subjects randomized with secukinumab in both phases will be considered. For more details, refer to Section 9. Safety will be evaluated by tabulations of adverse events and will be presented with descriptive statistics at each visit for each treatment group. The statistical evaluations will be organized by Treatment Phase (Weeks 0-16 and 16-48), and Post-Treatment Phase (weeks 48-52), as appropriate. AEs will be coded using the CTCAE, Common Terminology Criteria for Adverse Events, V 4.03. The number and percentage of subjects experiencing an AE/SAE will be stratified by system organ class, or a preferred term, and severity of the adverse event, and recorded and tabulated overall by each sub-strata. For more details, refer to Section 9.

Key Words: Ichthyosis, secukinumab, IL-17, biologic, monoclonal antibody

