- Reduction in transepidermal water loss (TEWL), a functional measure of barrier, at weeks 16, 32 and 52
- Reduction in the Dermatology Life Quality Index (DLQI) at weeks 16, 32 and 52
- Reduction in the iQoL-32 index at weeks 16, 32 and 52

Reduction in the above assessments stratified by subtype, severity, and gender

These clinical indices will be assessed as per the Schedule of Assessments flowchart (Appendix 1) and require minimal input or time commitment from the study participants, but are critical to analyze trends with time.

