
6.1.10 TEWL and Tape Strips

TEWL will be performed at the biopsy and skin swab sites (nondominant arm and upper buttocks) to assess the skin barrier at visits 2-12. Tape strips will be also be obtained from ichthyosis subjects at baseline and weeks 8, 16, 32 and 52. Tape strips are purchased from CuDerm. Tape stripping will be performed on the dominant upper outer arm (same sites serially) using circular 2x2 or 3x3 cm transparent tape strips at lesional skin sites for each patient or unaffected skin site for controls. The tape strips will be used for detection of alterations of epidermal lipids and proteins in the outer stratum corneum of epidermis. We will be sending tape strips for proteomics and lipidomics analysis to the laboratories at Mt. Sinai/Rockefeller University medical center under the supervision of [name] and other designated laboratories. Alternating tape strips will be obtained for these analyses. Equal pressure will be applied to affected areas for 10 seconds. Up to 32 tape strips will be serially extracted on skin sites. Tape stripping is painless and, in our experience and that of the literature, has no adverse sequelae.

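### TEWL is defined as a reduction without a threshold, but section 9.3 names only a 50% TEWL responder tested by Fisher's exact test and gives no method for change in TEWL

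*Combined protocol and SAP*

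**What the plan says.** Section 2.1 lists among the secondary efficacy endpoints "Reduction in transepidermal water loss (TEWL), a functional measure of barrier, at weeks 16, 32 and 52". No cut-off is attached. Where that section wants a responder endpoint it states the cut-off: 50% and 75% for IASI, 2 points for CISI, 3 points for itch and pain, and "50% Reduction in the Bodemer score".

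Section 9.3, under the secondary efficacy analysis, says that for IASI50/IASI75 at week 16 "a Fisher's exact test for contingency tables analysis will be used". It continues: "The same approach will be used for all other binary outcomes, including a 2-point reduction in CISI". The examples end with "and a 50% reduction in TEWL", the only mention of TEWL in section 9. The mixed-effect model in section 9.3 is assigned to the composite IASI and to the mRNA expression data.

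The synopsis has a general sentence: "Differences in change over time between treatment and placebo will be assessed using a mixed-effect model repeated measures". It names no outcome, comes straight after the primary variables, and is followed by a reference to Section 9 for details.

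Section 6.1.10 schedules TEWL "to assess the skin barrier at visits 2-12". By Appendix 1 this means baseline and weeks 4, 8, 12 and 16 in the placebo-controlled period.

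**The concern.** The endpoint and its analysis do not match. A mean reduction and the proportion of subjects who reach a 50% reduction are different quantities, and a drug can shift the first clearly while moving few subjects past the second. As section 9.3 stands, the quantity defined in section 2.1 has no stated estimate or test, and the quantity that is tested has no definition in section 2.1 and no rationale.

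TEWL is the trial's functional measure of the skin barrier, and section 1.4 names the barrier defect among the features whose dependence on IL-17 the trial should clarify. Five repeated continuous measurements up to week 16 would be reduced to one yes/no per subject, in a trial with 20 subjects randomised per arm. A real effect on TEWL could be missed. Alternatively, the choice between the two analyses would be left open until the data are seen.

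**Working it through.** **1. The plan's own figure (section 9.5, composite IASI).** Inputs: baseline mean 28.9, SD 9.0, pre-post correlation 0.55, reductions of 40% vs 10%, two-sided alpha 0.05.

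- SD of change = 9.0 × √(2 × (1 − 0.55)) = 8.54; the plan uses 8.5.
- Difference = 0.30 × 28.9 = 8.67 points, so the standardised effect is 8.67/8.5 = 1.02.
- Two-sample t-test, 16 per arm: power 79.7%. The stated 80% reproduces.
- 16/(1 − 0.20) = 20 per arm. This also reproduces.

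**2. What the plan gives for TEWL.** No mean change, SD, correlation or expected responder rate. Everything below is therefore assumption. The first check borrows the IASI scenario, with the SD of change expressed relative to the baseline mean: 8.5/28.9 = 29.4%. The other scenarios vary the means and SD.

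**3. Method.** The percent reduction is taken as normal with mean μ and SD σ.

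- Responder probability: p = 1 − Φ((50 − μ)/σ).
- Fisher power: exact enumeration over both binomial distributions, two-sided at 0.05.
- Continuous power: non-central t with effect (μ₁ − μ₀)/σ. The t-test stands in for the week-16 contrast of the mixed model, as it does in section 9.5.

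For the borrowed scenario:

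- Secukinumab: p = 1 − Φ((50 − 40)/29.4) = 1 − Φ(0.34) = 36.7%.
- Placebo: p = 1 − Φ((50 − 10)/29.4) = 1 − Φ(1.36) = 8.7%.

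**4. Results.**

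| Assumed mean reduction, SD | Responders | Fisher vs t, 16 per arm | Fisher vs t, 20 per arm |
|---|---|---|---|
| 30% vs 5%, SD 25 | 21% vs 4% | 15% vs 78% | 25% vs 87% |
| 40% vs 10%, SD 29.4 (IASI values) | 37% vs 9% | 33% vs 80% | 46% vs 88% |
| 60% vs 20%, SD 29.4 | 63% vs 15% | 71% vs 96% | 84% vs 99% |
| 60% vs 20%, SD 20 | 69% vs 7% | 96% vs nearly 100% | 99% vs nearly 100% |

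A small effect far below the cut-off is worse still: 20% vs 0% with SD 20 gives Fisher 0.3% against 78% at 16 per arm. In every scenario tried, the responder test had less power. The loss is severe when mean reductions lie well below 50%, and small when the effect is large and the cut-off falls between the two arms.

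**The case against.** The strongest reply is that a continuous analysis is not excluded. The synopsis sentence on the mixed model is general enough to be read as covering TEWL, and the 50% responder could be an addition to that analysis. This stands in part: nothing says that the responder replaces change in TEWL, so a reader who infers that the plan forbids a continuous TEWL analysis goes too far. But the synopsis sentence names no outcome and defers to Section 9, and there TEWL appears only under Fisher's test. At best the plan permits two different TEWL analyses without choosing between them.

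Second, a reader might infer that TEWL is tested with a known fraction of its power. The documents do not support a figure. TEWL is an instrument reading, and there is no reason given to think that it behaves like IASI. Only the direction of the loss is consistent across the scenarios.

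Third, because section 9.3 does not name the Bodemer score, a reader might infer that "50% Reduction in the Bodemer score" has no analysis. That is wrong. The Fisher rule applies to all other binary outcomes, and its list is introduced as a set of examples, so the Bodemer responder is covered.

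Fourth, TEWL is not alone. Section 9.3 also names no method for change in IASI-E, IASI-S, CISI, Yale, DLQI, iQoL-32 or 5-D itch. This is fair and bears on how the repair is worded. TEWL differs in that section 9.3 assigns it to a responder analysis that section 2.1 does not define.

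**Conclusion.** The mismatch is real and can be read directly from sections 2.1 and 9.3: an endpoint without a threshold, a single named analysis at an unexplained 50% threshold, and no stated method for the change itself. It should be corrected before unblinding. Dichotomising costs power, but how much depends on TEWL inputs that the documents do not contain. With 16 per arm, the four tabulated scenarios run from 15% vs 78% to 96% vs nearly 100%, and the IASI planning values give 33% vs 80%. All assume normally distributed percent reductions and use a t-test in place of the mixed model. The consequence is confined to one of many secondary endpoints in a pilot study.

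**What to change.** In section 9.3, state that change from baseline in TEWL is analysed with the mixed model already specified for IASI, and that the secukinumab-placebo contrast is made at week 16. Report weeks 32 and 52 as change from baseline without a placebo comparison, because all subjects receive secukinumab from week 16. Either delete the 50% TEWL responder, or keep it as a supportive analysis with a reason for the threshold and a matching entry in section 2.1. The same sentence could name the other continuous secondary endpoints and so close that gap too.

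Two editorial changes can go in at the same time: list the 50% Bodemer reduction among the binary examples, and correct EASI-S to IASI-S.

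The cost is one or two sentences. No new data, visits or subjects are needed.
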